### 12.3 Changes to the clinical study protocol

The PI and other site personnel involved in the study must not implement any deviation from or changes to the CSP without agreement with the Sponsor and prior review and documented approval from the IEC, except where necessary to eliminate an immediate hazard to the subjects. All changes to the final CSP must be documented in a written protocol amendment. However, administrative changes are to be documented in the Sponsor file without requiring a protocol amendment.

 GALDERMA	Title 43CHSA1803 Clinical Study Protocol	Doc id MA-39381
--	--	---------------------------

Effective date: 2019-06-20 00:56

Effective

Version: 2.0

## 13 Financing, Indemnification, and Insurance

The CTA outlines the compensation and payment terms of the study. The CTA must be signed before the first subject is screened in the study. If there are differences between the CTA and the CSP regarding certain rights and obligations, the CTA is the prevailing document. Q-Med AB's obligations in this clinical study are covered by Galderma's global general liability program. An insurance certificate will be provided upon request. The institution/PI is obligated to maintain insurance coverage for their obligations in the clinical study according to the CTA.

## 14 Publication Policy

The PI's, institutions, and Q-Med AB's obligations regarding intellectual property rights, confidentiality, and publications are described in detail in the CTA.

The aim is to submit the results of this study for publication in the public database ClinicalTrials.gov and to a medical journal for a first joint publication of the results. Everyone who is to be listed as an author of the results of this multicentre study shall have made a substantial, direct, intellectual contribution to the work. Authorship will be based on (1) substantial contributions to the conception or design of the work; or the acquisition, analysis, or interpretation of data for the work; and (2) drafting the work or revising it critically for important intellectual content; and (3) final approval of the version to be published; and (4) agreement to be accountable for all aspects of the work in ensuring that questions related to the accuracy or integrity of any part of the work are appropriately investigated and resolved\*. Conditions 1, 2, 3, and 4 must all be met in order to be designated as author. Those who do not meet all four criteria should be acknowledged. Among the authors that fulfil the above mentioned criteria, one author will be appointed by Q-Med AB to take primary responsibility for the overall work as primary author.

\*Defining the role of authors and contributors, compiled by the International Committee of Medical Journal Editors (ICMJE) (<http://www.icmje.org>).

## 15 Suspension or Premature Termination

The Sponsor will suspend or terminate the study when so instructed by the IEC or if it is judged that the subjects are subjected to unreasonable risks, or for valid scientific or administrative reasons.

The Sponsor may also decide to close a single study site due to unsatisfactory subject enrolment or non-compliance with the CSP, GCP, or applicable regulatory requirements.

In the event of premature termination, Q-Med AB will provide information on the handling of currently enrolled subjects who have not completed the study

 GALDERMA	Title 43CHSA1803 Clinical Study Protocol	Doc id MA-39381
--	--	---------------------------

## 17 Appendices

- Appendix 1 Declaration of Helsinki
- Appendix 2 Photo guide for MMVS

Title

43CHSA1803 Clinical Study Protocol

Doc id

MA-39381  
Appendix 1

## Declaration of Helsinki

### WMA Declaration of Helsinki - Ethical Principles for Medical Research Involving Human Subjects

Adopted by the 18th WMA General Assembly, Helsinki, Finland, June 1964 and amended by the:  
 29th WMA General Assembly, Tokyo, Japan, October 1975  
 35th WMA General Assembly, Venice, Italy, October 1983  
 41st WMA General Assembly, Hong Kong, September 1989  
 48th WMA General Assembly, Somerset West, Republic of South Africa, October 1996  
 52nd WMA General Assembly, Edinburgh, Scotland, October 2000  
 53rd WMA General Assembly, Washington DC, USA, October 2002 (Note of Clarification added)  
 55th WMA General Assembly, Tokyo, Japan, October 2004 (Note of Clarification added)  
 59th WMA General Assembly, Seoul, Republic of Korea, October 2008  
 64th WMA General Assembly, Fortaleza, Brazil, October 2013

#### Preamble

1. The World Medical Association (WMA) has developed the Declaration of Helsinki as a statement of ethical principles for medical research involving human subjects, including research on identifiable human material and data.

The Declaration is intended to be read as a whole and each of its constituent paragraphs should be applied with consideration of all other relevant paragraphs.

2. Consistent with the mandate of the WMA, the Declaration is addressed primarily to physicians. The WMA encourages others who are involved in medical research involving human subjects to adopt these principles.

#### General Principles

3. The Declaration of Geneva of the WMA binds the physician with the words, "The health of my patient will be my first consideration," and the International Code of Medical Ethics declares that, "A physician shall act in the patient's best interest when providing medical care."
4. It is the duty of the physician to promote and safeguard the health, well-being and rights of patients, including those who are involved in medical research. The physician's knowledge and conscience are dedicated to the fulfilment of this duty.
5. Medical progress is based on research that ultimately must include studies involving human subjects.
6. The primary purpose of medical research involving human subjects is to understand the causes, development and effects of diseases and improve preventive, diagnostic and therapeutic interventions (methods, procedures and treatments). Even the best proven interventions must be evaluated continually through research for their safety, effectiveness, efficiency, accessibility and quality.
7. Medical research is subject to ethical standards that promote and ensure respect for all human subjects and protect their health and rights.
8. While the primary purpose of medical research is to generate new knowledge, this goal can never take precedence over the rights and interests of individual research subjects.
9. It is the duty of physicians who are involved in medical research to protect the life, health, dignity, integrity, right to self-determination, privacy, and confidentiality of personal information of research subjects. The responsibility for the protection of research subjects must always rest with the physician

## Declaration of Helsinki

or other health care professionals and never with the research subjects, even though they have given consent.

10. Physicians must consider the ethical, legal and regulatory norms and standards for research involving human subjects in their own countries as well as applicable international norms and standards. No national or international ethical, legal or regulatory requirement should reduce or eliminate any of the protections for research subjects set forth in this Declaration.
11. Medical research should be conducted in a manner that minimises possible harm to the environment.
12. Medical research involving human subjects must be conducted only by individuals with the appropriate ethics and scientific education, training and qualifications. Research on patients or healthy volunteers requires the supervision of a competent and appropriately qualified physician or other health care professional.
13. Groups that are underrepresented in medical research should be provided appropriate access to participation in research.
14. Physicians who combine medical research with medical care should involve their patients in research only to the extent that this is justified by its potential preventive, diagnostic or therapeutic value and if the physician has good reason to believe that participation in the research study will not adversely affect the health of the patients who serve as research subjects.
15. Appropriate compensation and treatment for subjects who are harmed as a result of participating in research must be ensured.

### Risks, Burdens and Benefits

16. In medical practice and in medical research, most interventions involve risks and burdens. Medical research involving human subjects may only be conducted if the importance of the objective outweighs the risks and burdens to the research subjects.
17. All medical research involving human subjects must be preceded by careful assessment of predictable risks and burdens to the individuals and groups involved in the research in comparison with foreseeable benefits to them and to other individuals or groups affected by the condition under investigation.

Measures to minimise the risks must be implemented. The risks must be continuously monitored, assessed and documented by the researcher.

18. Physicians may not be involved in a research study involving human subjects unless they are confident that the risks have been adequately assessed and can be satisfactorily managed.

When the risks are found to outweigh the potential benefits or when there is conclusive proof of definitive outcomes, physicians must assess whether to continue, modify or immediately stop the study.

### Vulnerable Groups and Individuals

19. Some groups and individuals are particularly vulnerable and may have an increased likelihood of being wronged or of incurring additional harm.
- All vulnerable groups and individuals should receive specifically considered protection.
20. Medical research with a vulnerable group is only justified if the research is responsive to the health needs or priorities of this group and the research cannot be carried out in a non-vulnerable group. In

Title

43CHSA1803 Clinical Study Protocol

Doc id

MA-39381  
Appendix 1

## Declaration of Helsinki

addition, this group should stand to benefit from the knowledge, practices or interventions that result from the research.

### **Scientific Requirements and Research Protocols**

21. Medical research involving human subjects must conform to generally accepted scientific principles, be based on a thorough knowledge of the scientific literature, other relevant sources of information, and adequate laboratory and, as appropriate, animal experimentation. The welfare of animals used for research must be respected.
22. The design and performance of each research study involving human subjects must be clearly described and justified in a research protocol.

The protocol should contain a statement of the ethical considerations involved and should indicate how the principles in this Declaration have been addressed. The protocol should include information regarding funding, sponsors, institutional affiliations, potential conflicts of interest, incentives for subjects and information regarding provisions for treating and/or compensating subjects who are harmed as a consequence of participation in the research study.

In clinical trials, the protocol must also describe appropriate arrangements for post-trial provisions.

### **Research Ethics Committees**

23. The research protocol must be submitted for consideration, comment, guidance and approval to the concerned research ethics committee before the study begins. This committee must be transparent in its functioning, must be independent of the researcher, the sponsor and any other undue influence and must be duly qualified. It must take into consideration the laws and regulations of the country or countries in which the research is to be performed as well as applicable international norms and standards but these must not be allowed to reduce or eliminate any of the protections for research subjects set forth in this Declaration.

The committee must have the right to monitor ongoing studies. The researcher must provide monitoring information to the committee, especially information about any serious adverse events. No amendment to the protocol may be made without consideration and approval by the committee. After the end of the study, the researchers must submit a final report to the committee containing a summary of the study's findings and conclusions.

### **Privacy and Confidentiality**

24. Every precaution must be taken to protect the privacy of research subjects and the confidentiality of their personal information.

### **Informed Consent**

25. Participation by individuals capable of giving informed consent as subjects in medical research must be voluntary. Although it may be appropriate to consult family members or community leaders, no individual capable of giving informed consent may be enrolled in a research study unless he or she freely agrees.
26. In medical research involving human subjects capable of giving informed consent, each potential subject must be adequately informed of the aims, methods, sources of funding, any possible conflicts of interest, institutional affiliations of the researcher, the anticipated benefits and potential risks of the study and the discomfort it may entail, post-study provisions and any other relevant aspects of the study. The potential subject must be informed of the right to refuse to participate in the study or to withdraw consent to participate at any time without reprisal. Special attention should be given to the specific information needs of individual potential subjects as well as to the methods used to deliver the information.

Title

43CHSA1803 Clinical Study Protocol

Doc id

MA-39381

## Appendix 1

### Declaration of Helsinki

After ensuring that the potential subject has understood the information, the physician or another appropriately qualified individual must then seek the potential subject's freely-given informed consent, preferably in writing. If the consent cannot be expressed in writing, the non-written consent must be formally documented and witnessed.

All medical research subjects should be given the option of being informed about the general outcome and results of the study.

27. When seeking informed consent for participation in a research study the physician must be particularly cautious if the potential subject is in a dependent relationship with the physician or may consent under duress. In such situations the informed consent must be sought by an appropriately qualified individual who is completely independent of this relationship.
28. For a potential research subject who is incapable of giving informed consent, the physician must seek informed consent from the legally authorised representative. These individuals must not be included in a research study that has no likelihood of benefit for them unless it is intended to promote the health of the group represented by the potential subject, the research cannot instead be performed with persons capable of providing informed consent, and the research entails only minimal risk and minimal burden.
29. When a potential research subject who is deemed incapable of giving informed consent is able to give assent to decisions about participation in research, the physician must seek that assent in addition to the consent of the legally authorised representative. The potential subject's dissent should be respected.
30. Research involving subjects who are physically or mentally incapable of giving consent, for example, unconscious patients, may be done only if the physical or mental condition that prevents giving informed consent is a necessary characteristic of the research group. In such circumstances the physician must seek informed consent from the legally authorised representative. If no such representative is available and if the research cannot be delayed, the study may proceed without informed consent provided that the specific reasons for involving subjects with a condition that renders them unable to give informed consent have been stated in the research protocol and the study has been approved by a research ethics committee. Consent to remain in the research must be obtained as soon as possible from the subject or a legally authorised representative.
31. The physician must fully inform the patient which aspects of their care are related to the research. The refusal of a patient to participate in a study or the patient's decision to withdraw from the study must never adversely affect the patient-physician relationship.
32. For medical research using identifiable human material or data, such as research on material or data contained in biobanks or similar repositories, physicians must seek informed consent for its collection, storage and/or reuse. There may be exceptional situations where consent would be impossible or impracticable to obtain for such research. In such situations the research may be done only after consideration and approval of a research ethics committee.

#### Use of Placebo

33. The benefits, risks, burdens and effectiveness of a new intervention must be tested against those of the best proven intervention(s), except in the following circumstances:

Where no proven intervention exists, the use of placebo, or no intervention, is acceptable; or

Where for compelling and scientifically sound methodological reasons the use of any intervention less effective than the best proven one, the use of placebo, or no intervention is necessary to determine the efficacy or safety of an intervention

 GALDERMA	Title 43CHSA1803 Clinical Study Protocol	Doc id MA-39381
--	--	---------------------------

## Appendix 1

### Declaration of Helsinki

and the patients who receive any intervention less effective than the best proven one, placebo, or no intervention will not be subject to additional risks of serious or irreversible harm as a result of not receiving the best proven intervention.

Extreme care must be taken to avoid abuse of this option.

#### Post-Trial Provisions

34. In advance of a clinical trial, sponsors, researchers and host country governments should make provisions for post-trial access for all participants who still need an intervention identified as beneficial in the trial. This information must also be disclosed to participants during the informed consent process.

#### Research Registration and Publication and Dissemination of Results

35. Every research study involving human subjects must be registered in a publicly accessible database before recruitment of the first subject.
36. Researchers, authors, sponsors, editors and publishers all have ethical obligations with regard to the publication and dissemination of the results of research. Researchers have a duty to make publicly available the results of their research on human subjects and are accountable for the completeness and accuracy of their reports. All parties should adhere to accepted guidelines for ethical reporting. Negative and inconclusive as well as positive results must be published or otherwise made publicly available. Sources of funding, institutional affiliations and conflicts of interest must be declared in the publication. Reports of research not in accordance with the principles of this Declaration should not be accepted for publication.

#### Unproven Interventions in Clinical Practice

[figure not shown]
37. In the treatment of an individual patient, where proven interventions do not exist or other known interventions have been ineffective, the physician, after seeking expert advice, with informed consent from the patient or a legally authorised representative, may use an unproven intervention if in the physician's judgement it offers hope of saving life, re-establishing health or alleviating suffering. This intervention should subsequently be made the object of research, designed to evaluate its safety and efficacy. In all cases, new information must be recorded and, where appropriate, made publicly available.

## **Appendix 2**

### **Photo guide for MMVS**

#### **Medicis Midface Volume Scale**

©2016 Galderma

 GALDERMA	Title 43CHSA1803 Clinical Study Protocol	Doc id MA-39381
--	--	---------------------------

2019-06-20 00:56

Effective date:

*Effective*

Version: 2.0

1.1 Background

1.1.1 Study design

This is a randomized, multi-center, evaluator-blinded, no-treatment controlled study of Sculptra for correction of Midface Volume Deficit and/or Midface Contour Deficiency in subjects of Chinese origin, men or women aged 18 years or older.

For Group A, after screening, eligible subjects will be treated from day 1 and followed up for 24 months.

For Group B, the study includes two phases as follows:

Main study phase: It is randomized, evaluator-blinded and no-treatment controlled. After screening, all eligible subjects will be randomized either to the Treatment Group or the Control Group in a 2:1 ratio. All the subjects will be followed up for 12 months.

Extension study phase: After the main study phase, the Treatment Group and Group A will be followed up for additional 12 months.

Each Treating Investigator will enroll 1 or 2 subjects as Group A. Before start of enrolment into Group B, the injection technique will be evaluated by the Sponsor or designee of Sponsor and performed after the subjects in Group A for each investigator have received their first treatment and second treatment. If treatments are found to be correctly performed, no further training is needed, there are no outstanding questions regarding the injection technique and no other corrective actions are identified, the enrolment in Group B can start for that investigator.

Each subject assigned to Group A and Treatment Group will receive up to 4 injection sessions with 5 (± 1) weeks intervals. Study treatments should be stopped if optimal midface augmentation has been obtained or a maximum of 4 injection sessions completed. Optimal midface augmentation is defined as the best possible aesthetic result that can be obtained for an individual study participant, as agreed upon by the treating investigator and subject.

Subjects assigned to the Control Group will not receive treatment during the study.

For more details regarding the study, and references, see the Clinical Study Protocol (MA-39381).

1.1.2 Number of subjects and randomization

The study will be performed at approximately 8 sites in China and approximately 32 subjects in Group A and 189 subjects in group B will be enrolled. Approximately 189 subjects in group B will be randomized in a 2:1 ratio to treatment with Sculptra (Treatment Group) or to no treatment (Control Group). The randomization list will be stratified by site.

1.2 Study objectives

- To evaluate the effectiveness of Sculptra in the treatment of Midface Volume Deficit and/or Midface Contour Deficiency.
- To evaluate the safety of Sculptra in the treatment of Midface Volume Deficit and/or Midface Contour Deficiency.

	
Title 43CHSA1803 Statistical Analysis Plan - Sculptra China
	
Doc id MA-40407

--	---	-----------------------------------

1.3 Effectiveness assessments

For all assessments regarding subjects in Group A and subjects in Treatment Group in Group B, baseline will be defined as the observation that is closest to but prior to study treatment on Day 1. Likewise, change from baseline will be calculated as the value at a given time point minus the baseline value. For the Control Group baseline is defined as the observation that is closest to but prior to randomization.

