#### 4.4.2 Blinding

Only the evaluator will be blinded, both treating investigator and subjects will be open-labelled.

The Blinded Evaluator shall not be allowed to retrieve study supplies or to be present during opening of the study supplies or injections. The Treating Investigator is not allowed to discuss treatments with the blinded evaluator or the subjects. All documents with information on study products shall be kept in a separate binder not available to the blinded evaluator.

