#### 4.7 Schedule of events

**Table 1. Schedule of Events for Group A and Treatment Group**

	Screening	Baseline / Treatment 1	Treatment 2 (Optional) b	Treatment 3 (Optional) b	Treatment 4 (Optional) b	Follow-up	Follow-up	Final visit / Early termination
	D-21 to D1	D1	5W( $\pm 1w$ ) after treatment 1	5W( $\pm 1w$ ) after treatment 2	5W( $\pm 1w$ ) after treatment 3	5W( $\pm 1w$ ) after Last treatment	6M ( $\pm 2w$ ), 9M ( $\pm 2w$ ), 12M ( $\pm 2w$ ), and 18M ( $\pm 3w$ ) after Baseline	24M ( $\pm 4w$ ) after Baseline
Informed consent	X							
Demography	X							
Height		X						
Weight		X					X	X
Medical history & concurrent diseases	X	X a						
Concomitant medication/procedures	X	X a	X	X	X	X	X	X
Vital signs		X c						
Laboratory tests	X						X d	X e
Pregnancy test for childbearing potential women	X	X a,c	X c	X c	X c			X
Inclusion and Exclusion criteria	X	X a						
Randomization		X						

Treatment		X	X	X	X			
MMVS (Blinded Evaluator)	X	X a,c					X	X
MMVS (treating investigator)	X	X a,c	X c	X c	X c	X	X	X
Photography		X c	X c	X c	X c	X	X	X
GAIS (Treating investigator and Subject)			X c	X c	X c	X	X	X
Subject satisfaction questionnaire							X	X
Dispense subject diary		X	X	X	X			
Review and collect subject diary			X	X	X	X		
Device deficiencies		X	X	X	X			
Assessment of AE	X	X a	X	X	X	X	X	X
Study termination								X

- a) Omitted if screening and baseline visit occur on the same day.
- b) The visit is omitted if optional treatment was not performed.
- c) Performed prior to treatment.
- d) Only performed at 12M.
- e) Only performed at early termination if termination occurs before 12M visit.

	
Title 43CHSA1803 Clinical Study Protocol
	
Doc id MA-39381

--	--	-----------------------------------

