**Table 2. Schedule of Events for Control Group**

	Screening	Baseline	Follow-up	Final visit / Early termination
	D-21 to D1	D1	6M( $\pm 2w$ ) and 9M ( $\pm 2w$ ) after Baseline	12M ( $\pm 2w$ ) after Baseline
Informed consent	X			
Demography	X			
Height		X		
Weight		X	X	X
Medical history & concurrent diseases	X	X a		
Concomitant medication/procedures	X	X a	X	X
Vital signs		X		
Laboratory tests	X			
Pregnancy test for childbearing potential women	X			
Inclusion and Exclusion criteria	X	X a		
Randomization		X		
MMVS (Blinded Evaluator)	X	X a	X	X
MMVS (treating investigator)	X	X a	X	X
Photography		X	X	X
GAIS (Treating investigator and Subject)			X	X
Assessment of AE	X	X a	X	X
Study termination				X

a) Omitted if screening visit and baseline visit occur on the same day.

 GALDERMA	Title 43CHSA1803 Clinical Study Protocol	Doc id MA-39381
--	--	---------------------------

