#### 5.4 Screening and Subject Numbers

Each screened subject will be assigned a screening number consisting of "S" and the site number followed by a consecutive number starting with 01 at each site, e.g. S101, S102. The screening number shall be listed on a subject screening and inclusion log.

A "screening failure" is defined as a subject who does not fulfil the eligibility criteria. For screening failures, the eCRF screening visit shall be completed to an extent that makes it clear which assessments have been made and the reason why the subject did not fulfil the eligibility criteria. The reason for excluding a subject from entering the study shall also be specified in the subject screening and inclusion log.

When the Investigator has confirmed that all inclusion criteria and no exclusion criteria are met, each enrolled subject will be assigned a subject number by the eCRF. For group A, consisting of a capital letter A, the site number, then followed by a consecutive number starting with 001 at each site, e.g. A1001, A1002; for group B, consisting of the site number followed by a consecutive number starting with 001 at each site, e.g. 1001, 1002.

 GALDERMA	Title 43CHSA1803 Clinical Study Protocol	Doc id MA-39381
--	--	---------------------------

Effective date: 2019-06-20 00:56

The subject number, subject name, and other information sufficient to link the eCRF to the medical records (e.g. national identification number, chart number, etc.) shall be recorded on a subject identification list. The subject identification list shall only be available at the site, both throughout and after the study.

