## 7.2 Photography

Digital photographs will be taken of each subject pre-treatment at visits when treatment is performed and at each follow-up visit. Standardized 3D photographs will be achieved for effectiveness assessment. 2D photographs will be used to document condition at baseline, for GAIS evaluation and to document AEs in the treated area. If necessary, the photo should be taken when AEs occur.

Photographs will be taken in a standardized way according to the instructions for image procedures. The subject shall have a neutral facial expression and no covering make-up should be used on the photographs.

Each Investigator and other study site personnel designated to take photographs, if applicable, shall be thoroughly trained in the equipment and techniques, and how to upload photographs to the secured web portal, if applicable, before study start. The same photographic equipment and standardized setting must be used at each visit (e.g., distance, light, facial position and expression). For further details, please see the instruction of image procedures in the photo user guide.

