2.4.4 Secondary effectiveness analysis

The percentage of responders based on the MMVS on both sides of the face concurrently will also be derived at all applicable follow-up visits for both the blinded evaluator's assessment and the treating investigator's assessment respectively. The response rates and their 95% confidence interval will be presented by visit and group.

Fisher's exact test will be used to compare the response rates in the Treatment group versus the Control group based on the blinded evaluator's assessment and the treating investigator's assessment respectively. In other words, the null hypothesis

$H_0: \pi_{t,Sculptra} = \pi_{t, Control}$ will be tested against the alternative hypothesis

$H_1: \pi_{t,Sculptra} \neq \pi_{t, Control}$ for each of the timepoints $t =$ Month 6 and Month 9 for the blinded evaluator's assessment, and $t =$ Month 6, Month 9 and Month 12 for the treating investigator's assessment.

The volume change in the midface area as compared with baseline (right and left sides combined) obtained by 3D imaging will be presented descriptively by treatment for all applicable follow-up visits.

GAIS (by treating investigator and subject) and satisfaction with the treatment outcome will be analyzed descriptively.

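### SAP 1.3 anchors baseline to treatment for Sculptra and to randomisation for control, and nothing requires Day 1 MMVS or photographs to precede randomisation, so the arms can end up with different baselines and controls with no qualifying 3D image

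*SAP*

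**What the plan says.** SAP 1.3 (Effectiveness assessments) gives two rules. For Group A and the Sculptra arm of Group B, "baseline will be defined as the observation that is closest to but prior to study treatment on Day 1". For the other randomised arm: "For the Control Group baseline is defined as the observation that is closest to but prior to randomization". SAP 2.1 says the SAP overrides the protocol's statistical sections where they differ, so these rules govern every change-from-baseline endpoint.

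On the order of Day 1 procedures, the protocol says the following.

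- **Sculptra arm.** Table 1 marks Day 1 MMVS and photography with footnote c, "Performed prior to treatment". Section 4.8.1.2 repeats this and names randomisation ahead of both.
- **Control arm.** Table 2 and section 4.8.2.2 give no timing qualifier. The list again names randomisation ahead of photography and MMVS.
- **Photographs.** Section 7.2 ties them to treatment and follow-up: "Digital photographs will be taken of each subject pre-treatment at visits when treatment is performed and at each follow-up visit". Neither schedule has a photograph at screening.
- **Same-day screening and baseline.** Day 1 MMVS carries the footnote "Omitted if screening visit and baseline visit occur on the same day". Photography does not.
- **Eligibility.** Section 5.4: "When the Investigator has confirmed that all inclusion criteria and no exclusion criteria are met, each enrolled subject will be assigned a subject number".
- **Blinding.** Section 4.4.2: "Only the evaluator will be blinded, both treating investigator and subjects will be open-labelled".

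**The concern.** In a randomised comparison, baseline should be the same observation, chosen by the same rule, in both arms. Here the rule differs by arm. Whether the two rules pick the same observation depends on a sequence that the documents do not fix.

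Three things depend on it:

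- **3D volume change** needs a baseline image in both arms. It is a listed secondary endpoint with control values planned at Months 6, 9 and 12.
- **Treating investigator's MMVS response** is tested at Months 6, 9 and 12. These are three of the five secondary Fisher tests; the other two are the blinded evaluator's at Months 6 and 9. A baseline scored after allocation is known, in one arm only, adds an avoidable source of bias.
- **Blinded evaluator's baseline MMVS** feeds the primary responder definition, the hot-deck classes (SAP 2.4.2) and a per-protocol exclusion (SAP Table 3).

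**Working it through.** The plan gives no figure on this point, so the check applies the two SAP rules to the two schedules.

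**Inputs.** The rules come from SAP 1.3. The scheduled assessments come from Tables 1 and 2: MMVS at screening and on Day 1, with Day 1 omitted for same-day visits; photographs on Day 1 but not at screening. The gap between visits is 0 to 21 days (protocol 4.3).

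**Which observation each rule selects (Sculptra / control):**

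| Screening and baseline | Day 1 assessment relative to randomisation | MMVS baseline | 3D baseline image |
|---|---|---|---|
| Same day | Before | Single rating / single rating | Day 1 / Day 1 |
| Same day | After | Single rating / single rating | Day 1 / none |
| Separate days | Before | Day 1 / Day 1 | Day 1 / Day 1 |
| Separate days | After | Day 1 / screening | Day 1 / none |

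These are logical cases, not frequencies. MMVS and photography can be ordered independently, so the last two columns should be read separately.

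**Do the documents settle the order?**

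1. The visit lists put randomisation first in both arms, but neither is declared to be a sequence.
2. A before-treatment requirement does not imply before randomisation. The Day 1 pregnancy test shows this: it carries the same footnote c in Table 1 but is not scheduled for controls in Table 2. In Group B it can therefore be limited to the Sculptra arm only if allocation is already known.
3. For MMVS there is some evidence that it comes first. Eligibility is re-checked at baseline alongside a second blinded rating, and the subject number follows confirmed eligibility. SAP Table 3-12 and the hot-deck classes list only baseline scores 2, 3 and 4. But the screening rating can also satisfy eligibility, so this is support, not a rule.
4. For photographs there is no such evidence. They are not an eligibility measure, and they are not dropped or moved for same-day visits.

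The control image is therefore the firmest part of the point. The MMVS difference needs two conditions together: separate visits, and a Day 1 rating after randomisation.

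**The case against.** The strongest reply is that the two anchors are natural. Controls have no treatment to anchor to, so randomisation is the Day 1 event that stands in for it. A rule asking for a control observation before randomisation presupposes that everyone is assessed first, and the rules then agree. The control visit with photography is itself named baseline, and controls receive nothing that day, so an image taken shortly after randomisation shows the same untreated face. A sensible programmer would use it. The 3D result is in any case only "obtained by 3D imaging will be presented descriptively by treatment for all applicable follow-up visits". The treating investigator is open-label at every follow-up, so that comparison is unblinded whatever the baseline order, and the same rater's screening score is available as a check.

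Much of this stands. No bias is shown, and an order that makes the rules agree is quite possible. What does not stand is that the text already implies that order: the pregnancy test shows that a before-treatment procedure can follow randomisation. Using the post-randomisation control image is sensible, but it departs from the SAP rule as written.

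Three stronger readings are tempting, and the documents do not support them:

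- **The visit lists prove that randomisation comes first.** They are lists of procedures, with no stated sequence.
- **Control 3D data will be lost.** That requires photographs to follow randomisation and the only scheduled baseline image to be discarded.
- **The primary comparison is biased.** The blinded evaluator's Day 1 rating probably precedes randomisation. If it does not, one can argue that a qualifying screening score would favour later apparent improvement in controls, and so work against Sculptra, but the documents give no rating-repeatability figure to size this.

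**Conclusion.** The point holds as a defect in a stated rule, not as a demonstrated bias. SAP 1.3 uses different anchors in the two randomised arms. Applied literally in the listed order of procedures, it leaves controls without a qualifying 3D baseline image. With separate visits, it also takes MMVS baselines from different visits in the two arms.

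The size cannot be estimated from the documents: neither the share of subjects in each visit order nor the effect of a shifted rating is given. The most plausible effect on the primary endpoint is zero. For the treating investigator's tests, fixing the baseline removes one avoidable source of bias and leaves the open-label follow-up as it is. The planned sample size and significance level are not affected. The point is worth correcting because it leaves baseline to be settled at programming, and one common rule costs little.

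**What to change.** Use one baseline rule for both Group B arms in SAP 1.3, and keep the pre-treatment rule for Group A.

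- **Going forward.** State in protocol 4.8.1.2 and 4.8.2.2 that both raters' MMVS and the photographs are completed before randomisation. In SAP 1.3, define baseline for both arms as the last assessment before randomisation. Make these edits together: the SAP edit alone would disqualify any Sculptra image taken after randomisation but before treatment, which qualifies now.
- **Subjects already randomised in another order.** State in the SAP that the Day 1 assessment is baseline in both arms: before treatment in the Sculptra arm, and the screening rating where both visits fell on the same day.

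Cost: no added visit, procedure or subject. The protocol edit is a written amendment that needs ethics committee approval (protocol 12.3), so it is more than a wording change. The SAP can be amended before database lock (SAP 2.1). If an amendment is not wanted, the SAP sentence on the Day 1 assessment resolves the missing control image by itself and gives both arms the same anchor. It does not stop the treating investigator from scoring baseline with the allocation known.
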